6.5.2. Method of Assigning Patients to Treatment Groups

Randomization will be performed centrally via a centralized telephone Interactive Voice Response System (IVRS) at the Leuven Coordinating Centre for Clinical Trials with the use of a computer-generated assignment sequence. Patients will be stratified according to the presence of an initial shockable rhythm.

6.5.3. Prior and Concomitant Therapy

All patients will be treated according to the current American heart association guidelines (*Peberdy et al, Circulation 2010*). All patients should be intubated, mechanically ventilated and sedated with propofol and remifentanil if hemodynamically tolerated. Cisatracurium should be administrated in case of shivering during hypothermia and continued until the end of the 36 hours study period once started. Doses of sedative and analgetic drugs or muscle relaxants will be reassessed at least once every eight hours to achieve values ranging from -3 to 0 on the Richmond Agitation-Sedation scale (which ranges from -5 to 4 with lower scores indicating deeper sedation and higher scores indicating increasing agitation). Unless an obvious non-cardiac cause can be identified, all patients should be referred for urgent coronary angiography for prompt revascularization of severe culprit coronary lesions. Basic infusions will include glucose 5% (40 ml/hr) and balanced crystalloids (40ml/hr).

Therapeutic hypothermia will be induced in all patients by endovascular (Icy-catheter, CoolGard® 3000, Alsius, Irvine, CA, USA) or surface (ArcticGelTM pads, Arctic Sun® 5000, Medivance, Louisville, Colorado, USA) cooling systems at 33°C for 24-hours as per existing ESC/AHA guidelines. After rewarming (0.3°C/hr) until 36°C, further targeted temperature management to avoid fever will be applied for 36 hours by antipyretic drugs and mechanical cooling devices.

Mechanical ventilation will be adjusted guided by hourly blood gas analysis to target a PaCO₂ between 35-45mmHg and a PaO₂ between 70-150mmHg. In principle, extreme low-tidal volume will be avoided to exclude interference with stroke volume variation measurements. Sedation will be titrated towards patient's comfort. Patients will be extubated after sufficient neurological (GCS>8/15), respiratory (successful spontaneous breathing trial) and hemodynamic recovery. A uniform and detailed protocol for mandatory testing of these parameters will be implemented at both recruiting sites.

6.5.4. Treatment Compliance

It is the principal investigators responsibility to ensure that the treatment, as detailed in the approved protocol, is administered to each enrolled subject. All patients will be treated under the principal investigator's (or responsible sub-investigator) direct supervision. All drug used in the study must be accounted for and documented in a usage log.

6.6. Recordings during treatment period

6.6.1. Continuous automatic recordings

- **All patients:**
 - o Continuous invasive arterial blood pressure (MAP, systolic, diastolic)
 - o Heart rate
 - o Oxygen saturation
 - o Cerebral saturation monitoring (FORE-SIGHT™ technology (CAS Medical systems, Branford, CT, USA). This information will be blinded to the treating physicians.
- **Intervention group:**
 - o Continuous Cardiac output (CCO) by Pulmonary Artery Catheter (PAC) (Edwards®, Irvine, California, USA)
 - o Continuous SVO₂ monitoring
 - o Continuous stroke volume variation (SVV) by radial artery vigileo
 - o Continuous Pulse pressure variation (PPV) by radial artery vigileo

6.6.2. Hourly automatic recordings

- **All patients:**
 - o Dose of norepinephrine
 - o Dose of dobutamine
 - o Dose of Isuprel (if applicable)
 - o Ventilator settings: FIO₂, PEEP, Tidal volume, respiratory frequency

6.6.3. Hourly manual recordings

- **All patients:**
 - o Blood gas analysis with determination of pH, p_aCO_2 , p_aO_2 , hemoglobin and lactate
 - o Adverse events:
 - Incidence of life threatening arrhythmias
 - Incidence of new onset atrial fibrillation
 - Incidence of pulmonary congestion requiring diuretics
 - Presence of limb ischemia
 - o If applicable
 - IABP ratio
 - Temporary pacing (Beats per minute)
- **Intervention group:**
 - o SVO_2 by blood gas per 4 hours to calibrate the continuous SVO_2 monitor

6.6.4. Daily recordings (day 0-5)

- **Clinical examination**
 - o Glasgow Coma Scale
 - o Pupil and cornea reflex
- **ECG**
- **Chest X-ray (pulmonary edema?)**
- **Urinary output**
- **Biochemistry**
 - o RBC count
 - o WBC count
 - o Hemoglobin
 - o Hematocrit
 - o INR
 - o Creatinine
 - o Urea
 - o Liver function
 - o Troponin
 - o Creatinine Kinase / (MB)

- C reactive protein
- Neuron specific enolase
- S-100B

Serum samples: All blood specimens will be collected, prepared and handled according to the guidelines provided by Gasthuisberg University Clinical Laboratory, the central blood chemistry laboratory or the laboratory for Experimental Cardiology.

6.6.5. *Other recordings*

- Day 1: Cardiac ultrasound with determination of the left ventricular ejection fraction (LVEF)
- Day 4: neurologic examination including EEG, SSEP
- Day 4-5: MRI with DWI
- Transcranial Doppler at 3,6,12,24, 36 and 48 hours in a subset of patients
- At ICU discharge: Cerebral performance category score
- At discharge from the hospital: Neurocognitive testing.
 - Wechsler memory scale (version IV)
 - Montreal cognitive assessment (version 7.2)
 - Wechsler adult intelligence scale
- At discharge from the hospital: Functional testing: Activities Daily Life (ADL) and 6 minute walking distance (6MWD)
- Length of stay in the ICU
- Duration of mechanical ventilation
- PGF2 alfa (as a marker of reactive oxygen species) will be measured on stored serum samples to be collected at baseline and after 24 hours

6.7. *Neurologic prognostication*

All patients will receive full ICU treatment until minimum 5 days after admission. At this point, a neurologist who is unaware of the intervention assignment will perform a standardized full neurologic evaluation and issue a recommendation for the continuation or withdrawal of therapy. The neurologic evaluation will be based on clinical signs (including GCS, pupillary and corneal reflexes), SSEP and EEG. Findings allowing for earlier discontinuation of active intensive care will be (1) patients with myoclonus

[figure not shown]
status during the first 24 hours after admission and a bilateral absence of N20-peak on SSEP and (2) patients who become brain death due to cerebral herniation. All clinical decisions will remain at the discretion of the treating team.

6.8. Efficacy and Safety Variables

6.8.1. Duration of Participation

It is expected that patients will participate in this study for 180 days, including 36 hours of treatment with study drug, cardiac MRI at day 4-5 and clinical follow-up until 180 days after CA.

Adverse events will be recorded during the period of study drug administration.

Visit schedule overview:

- At ICU discharge:
 - Cerebral performance category score
 - Length of ICU stay
 - Length of mechanical ventilation
 - Tracheostomy (yes/no)

- At hospital discharge
 - Cognitive testing
 - ADL
 - 6 MWD
 - Cerebral performance category score
- At 180 days post-CA
 - Cerebral performance category score
 - SF36

6.8.2. Assessment of outcome

- **Primary efficacy outcome:**

The primary outcome is the extent of cerebral ischemia as quantified by diffusion weighted MRI (DW-MRI) to be performed at day 4-5 with quantification of the percentage of ischemic voxels with an apparent diffusion coefficient (ADC) below 0.650 mm²/s.

- **Secondary efficacy outcomes:**

- Cerebral performance category 3-5 at discharge from the ICU
 CPC 1: return to normal cerebral function and normal living
 CPC 2: Disability but sufficient function for independent activities of daily life
 CPC 3: severe disability
 CPC 4: Coma
 CPC 5: Death
- Cerebral performance category 3-5 at 180 days post-CA (assessed by trial investigators that are unaware of the treatment assignment)
- SF36 questionnaire at 180 days post-CA (assessed by trial investigators that are unaware of the treatment assignment)
- Neurocognitive testing at discharge from the hospital
- Biomarkers: Neuron specific enolase (day 1-2-3-4-5)
- Functional testing: Activities Daily Life (ADL) and 6 minute walking distance (6MWD) at discharge from the hospital
- Renal function: creatinine day 1-2-3-4-5 and urinary output day 1-2-3-4-5.
- Length of stay in the ICU
- Duration of mechanical ventilation
- Placement of tracheostomy

- **Safety outcomes:**

- Incidence of life threatening arrhythmias during intervention period
- Incidence of new onset atrial fibrillation during intervention period
- Incidence of pulmonary congestion requiring diuretics during intervention period

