1. SYNOPSIS

Classification: Academic, Investigator Initiated Trial

Protocol Version and Date: Version 4, 20 Jan 2017

Title of Study: Neuroprotective goal directed hemodynamic optimization in post-cardiac arrest patients: a randomized controlled trial (the NEUROPROTECT post-CA trial)

Participating country: Belgium

Study Centers: 2 (UZ Leuven and ZOL Genk)

Study Period: 3 years

Anticipated start: July 2015

Anticipated completion: May 2018

Objectives:

The **primary objective** of the trial is to assess whether or not a new goal directed hemodynamic optimization strategy can reduce cerebral ischemia in post-cardiac arrest (CA) patients as quantified by diffusion weighted MRI (DW-MRI) to be performed at day 4-5 with quantification of the percentage of ischemic voxels with an apparent diffusion coefficient (ADC) below 0.650 mm²/s.

Secondary efficacy outcomes:

- Cerebral performance category 3-5 at discharge from the ICU CPC 1: return to normal cerebral function and normal living
CPC 2: Disability but sufficient function for independent activities of daily life
CPC 3: severe disability CPC 4: Coma
CPC 5: Death
- Cerebral performance category 3-5 at 180 days post-CA (assessed by trial investigators that are unaware of the treatment assignment)
- SF36 questionnaire at 180 days post-CA (assessed by trial investigators that are unaware of the treatment assignment)
- Neurocognitive testing at discharge from the hospital
- Biomarkers: Neuron specific enolase (day 1-2-3-4-5)

- Functional testing: Activities Daily Life (ADL) and 6 minute walking distance (6MWD) at discharge from the hospital
- Renal function: creatinine day 1-2-3-4-5 and urinary output day 1-2- 3-4-5.
- Length of stay in the ICU
- Duration of mechanical ventilation
- Placement of tracheostomy

Safety outcomes:

- Incidence of life threatening arrhythmias during intervention period
- Incidence of new onset atrial fibrillation during intervention period
- Incidence of pulmonary congestion requiring diuretics during intervention period

Methodology: Prospective, multi-centre, interventional open label investigator driven randomized controlled trial. Randomisation will be stratified by the presence of an initial shockable rhythm.

Number of subjects planned: A total of 112 pts are planned for this study.

Anticipated duration of trial: 3 years from first patient entered to last patient randomized

Diagnosis and main criteria for inclusion and exclusion:

Inclusion criteria:

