6.9. Statistical Methods Planned

6.9.1. Sample size

Based on the results of a pilot study at Stanford University in which the standard deviation of the percentage $ADC < 0.650 \text{ mm}^2/\text{s}$ in comparable post-CA patients was 8.9%, we estimated that 56 patients would be necessary in each study group to show a 40% reduction in the extent of cerebral ischemia with a power of 80% at a two-sided alpha level of 0.05.

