6.9.3. General statistics

All data will be managed by the LCC in conjunction with the Steering Committee. Data will be entered and reviewed on an ongoing basis. Key listings and tables will be defined by the Steering Committee. Tables, listings and raw data (as SAS transport files) will be made available to the members of the Steering Committee upon request.

The statistical analysis of the primary and all secondary efficacy endpoints will be performed in the modified Full Analysis Set (FAS), defined as all randomly assigned patients except those withdrawing informed consent for use of all trial data and in case many protocol violations are observed throughout the study, a Per Protocol Set (PPS) will be defined and all efficacy analyses will be repeated on the PPS.

All continuous data will be presented by treatment group using the number of non-missing observations, mean, standard deviation, median and (Q1,Q3). Categorical data will be presented by treatment group using the observed frequencies and percentages for each category.

The primary endpoint (% voxels with ADC < 0.650 mm²/s) will be analyzed by means of an analysis of variance (ANOVA) that includes randomized group and initial shockable rhythm as factors. The treatment effect will be estimated by the difference between treatment groups and presented along with its corresponding 95% confidence interval. Missing values for patients who die prior to the DW-MRI will be imputed on the basis of age, gender, presence of basic life support, presence of initial shockable rhythm, duration of advanced life support, neuron specific enolase, presence of a malign EEG pattern on day 1, final outcome at ICU discharge and allocated treatment arm.

Continuous and normally distributed secondary endpoints will be analyzed by means of an ANOVA including randomized treatment and initial shockable rhythm as factors in the model. Estimated treatment differences will be presented with their 95% confidence interval. Continuous secondary endpoints that show serious deviations from a normal distribution will be analyzed by means of a Van Elteren that includes the initial shockable rhythm as stratification factor. Binary secondary endpoints will be analyzed by means of a stratified Chi-squared test. Treatment differences will be expressed as risk ratios and presented along with their corresponding 95% confidence intervals.

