## 2 Study Objectives and Endpoints

### 2.1 Study Objective

The **primary objective** of the trial is to assess acute whether or not a new goal-directed hemodynamic optimization strategy can reduce cerebral ischaemia in post-cardiac arrest (CA) patients as quantified by diffusion weighted MRI (DW-MRI) to be performed at day 4-5 with quantification of the percentage of ischaemic voxels with an apparent diffusion coefficient (ADC) below 0.650 mm^2/s.

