### 2.2 Study Endpoints

#### 2.2.1 Primary Target Variable

% of ischaemic voxels with an ADC<0.650 mm^2/s on 4-5 day DW-MRI.

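### The cut-off that defines the primary endpoint is written as 0.650 mm²/s with no scale factor, which is far above any plausible ADC; most likely a 10⁻³ was omitted

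*Protocol*

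**What the plan says.** Protocol 6.8.2 defines the primary outcome by "quantification of the percentage of ischemic voxels with an apparent diffusion coefficient (ADC) below 0.650 mm²/s" on diffusion-weighted MRI at day 4-5. The synopsis and section 5 (Study Objectives) both state the cut-off as "apparent diffusion coefficient (ADC) below 0.650 mm²/s". The sample-size paragraph (6.9.1) uses the same number and unit, and so does the analysis paragraph (6.9.3): "The primary endpoint (% voxels with ADC < 0.650 mm²/s) will be analyzed by means of an analysis of variance (ANOVA".

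The SAP repeats it. Section 2.1 has "apparent diffusion coefficient (ADC) below 0.650 mm 2 /s", section 2.2.1 has "of ischaemic voxels with an ADC<0.650 mm 2 /s on 4-5 day DW-MRI", and section 5 restates it within the sample-size justification.

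That makes eight statements in two documents, all agreeing on 0.650 mm²/s. None carries a power of ten or a unit such as µm²/ms. SAP 11.4 (MRI Data) covers only the remaining MRI variables and says nothing about the scale of the ADC map. For the percentage itself, Protocol 6.9.1 reports that the pilot SD "in comparable post-CA patients was 8.9%, we estimated that 56 patients would be necessary in each study group", sized to show a 40% reduction.

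**The concern.** An ADC measures how freely water moves in tissue, so it should not exceed the diffusion of free water. In mm²/s that is a number in the thousandths. A cut-off of 0.650 in the same unit lies far above anything a scan of brain can return, measurement noise aside, so the condition of lying below it excludes nothing.

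The cut-off is what turns an image into the primary endpoint. The sample size, the ANOVA, the multiple imputation (SAP 7.4 and 10.1) and the seven subgroup analyses (SAP 7.8) all concern the percentage that it produces. Someone who processes the scans, audits the processing or repeats the trial from these documents would have to supply the scale from outside. Because the SAP repeats the protocol's figure, neither document holds a correct statement to fall back on.

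**Working it through.** **Inputs from the documents**
- Cut-off: 0.650 mm²/s (Protocol synopsis, 5, 6.8.2, 6.9.1, 6.9.3; SAP 2.1, 2.2.1, 5).
- Pilot SD of the percentage of voxels below it: 8.9%. Planned effect: 40% reduction. Size: 56 per group, 80% power, two-sided alpha 0.05 (Protocol 6.9.1; SAP 5).

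**Inputs assumed (general physical values, not in the documents)**
- Free water at body temperature: 3 × 10⁻³ mm²/s, range 2 to 4 × 10⁻³. Tissue does not exceed free water.
- For the last part of step 3 only, brain tissue: 0.6 to 1.0 × 10⁻³ mm²/s.

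**Step 1. Does the unit enter the plan's own figure?** The usual formula is n per group = 2 × (1.96 + 0.84)² × SD² / difference², with SD and difference both in percentage points of voxels. The ADC unit does not appear in it. The 56 cannot be reproduced from the stated inputs, because no control-group mean is given to turn 40% into a difference. Run backwards, it gives 2.80 × 8.9 × √(2/56) = 4.71 percentage points. Rescaling the cut-off leaves that unchanged.

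**Step 2. Written cut-off against the ceiling.**
- 0.650 / 0.004 = 163
- 0.650 / 0.003 = 217
- 0.650 / 0.002 = 325

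The written value is 163 to 325 times the ceiling. Even at the top of the range, the assumed constant would have to be too low by a factor of 163 before any voxel could lie above the cut-off. Read literally, the endpoint is 100% in every patient, with SD 0. A measure fixed at 100% cannot have an SD of 8.9% and cannot be reduced by 40%.

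**Step 3. Which power of ten is missing?** Steps 1 and 2 do not give a factor of 1000 by themselves. Trying successive powers of ten:
- × 10⁻¹: 0.065, still above 0.004 (ratio 16).
- × 10⁻²: 0.0065, still above 0.004 (ratio 1.6).
- × 10⁻³: 0.00065, below the ceiling throughout the range (0.00065 / 0.002 = 0.33; 0.00065 / 0.004 = 0.16).

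So 10⁻³ is the first power of ten that brings the cut-off under the ceiling. Against the assumed tissue values it gives 0.65 / 1.0 = 0.65 to 0.65 / 0.6 = 1.08, a position where it can separate voxels. A further factor of ten would give 0.065 to 0.11 of the tissue values, where few voxels would be expected to fall below it. This supports an omitted 10⁻³ but remains an inference.

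**Step 4. Could the factor have been lost in conversion of the files?** Unlikely. The squared exponent on mm is kept in all eight places and in both documents, so a factor with its own exponent would have had to vanish every time.

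**The case against.** The strongest reply is that this is a notation slip which reveals itself. Anyone who applied the literal value would get 100% in every patient and notice at once. The reported pilot SD shows that the pilot, at least, used a scale on which voxels separate, and the trial's readers probably did the same. The sample size, the randomisation, the imputation and the ANOVA are untouched. All of this stands, and it limits the practical harm.

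A second reply is that the documents do not contradict themselves unaided. The SD and the planned reduction show only that the endpoint varies. They conflict with 0.650 mm²/s only once a diffusion constant from outside is added. That also stands. The conclusion is nevertheless insensitive to the constant, which would have to be wrong by more than a hundredfold.

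Three stronger readings are tempting and are not supported. A reader might infer that the trial question cannot be answered; that would follow only if the literal value had been applied to the scans, and nothing in either document says so. A reader might infer that the sample size is wrong because of the unit; step 1 shows that the unit does not enter it. The unstated control mean is a separate matter and gives no evidence on the unit. A reader might also take the factor of exactly 1000 as proved; it is inferred, and the sponsor has to confirm it.

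**Conclusion.** The cut-off is wrong as written in all eight places. Assuming free water at 2 to 4 × 10⁻³ mm²/s as an upper limit for tissue, it is 163 to 325 times too high to separate any voxels. The literal endpoint would be constant at 100%, which under the same assumption cannot be squared with the pilot SD of 8.9% and the planned 40% reduction. The likely explanation is a unit or notation error, an omitted 10⁻³. No calculation in the plan is miscomputed, and the design and analysis model do not change. It still needs correcting, because this is the only definition of the sole primary endpoint and no other statement in either document fixes the scale.

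**What to change.** Ask those who processed the images which threshold and unit were actually applied to the ADC maps. This needs no outcome data by group, so blinding is not at risk. Then correct all eight statements: Protocol synopsis, 5, 6.8.2, 6.9.1 and 6.9.3; SAP 2.1, 2.2.1 and 5. The expected text is 0.650 × 10⁻³ mm²/s, equivalently 650 × 10⁻⁶ mm²/s. If the confirmed setting differs, state that setting instead.

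Make the correction before database lock, which SAP 4.2 treats as still to come, and record it with date and reason as Protocol 6.10 requires. The cost is wording only: no new data and no change to sample size or analysis.

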6.3. Selection of Study Population

All patients presenting or referred to the investigational site after being successfully resuscitated from out of hospital CA will be screened for enrolment. All patients will be expected to meet all inclusion and exclusion criteria before entering the study. Minor deviations to these criteria may be allowed with prior approval of the principle investigator of the study site.

6.3.1. *Inclusion Criteria*

The patient must meet the following criteria:

1. Out-of-hospital CA of presumed cardiac cause irrespective of the presenting rhythm
2. Unconsciousness (Glasgow coma scale < 8) at hospital admission
3. Age \geq 18 years
4. Sustained return of spontaneous circulation (ROSC) (=when chest compressions have not been required for 20 consecutive minutes)

6.3.2. *Exclusion Criteria*

Exclusion Criteria:

1. Suspected or confirmed intracranial bleeding or stroke
2. Known limitations in therapy or Do Not Resuscitate-order
3. Known disease compromising 180 day survival
4. Known pre-CA cerebral performance category 3-4
5. Previous stroke (TIA can be included)
6. MRI incompatible cardiac or neurosurgical device
7. Systolic blood pressure < 90 mmHg on norepinephrine > 1 mcg/kg/min).
8. Open chest
9. ECMO (extracorporeal membrane oxygenation)
10. Pregnancy

6.3.3. *Withdrawal of Patients from Therapy or crossover*

In the intervention (“Neuroprotect post-CA”) group, a reduction in vasopressor doses to maintain a MAP of 65mmHg is recommended if any of the pre-specified serious adverse events that were potentially related to an increased rate of vasopressor infusion occurs. These events include: major ventricular arrhythmia requiring life support, electrical or pharmacological cardioversion, poorly tolerated supraventricular arrhythmia and peripheral limb ischemia.

Treatment may also be discontinued if the legal representative withdraws their consent.

All patients who are withdrawn from study treatment will have safety assessments completed during the entire course of the study.

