SVO₂ < 65 %	
Step1: Fluid responsiveness?
 
 • Sinus: SVV > 12% • AF: Passive leg raising test 
7 Plasmalyte 500 cc/u (max 3l/24u)
 
Step2: Hemoglobin < 10 g/dl?
 
7 Transfusion 1 UPC
 
Step3: Heartrate < 40 SPM
 
7 Consider Isuprel of Pacing
 
Step4: Inotropics/vasopression
 
 • Dobutamine + 5 mcg/kg/min (max 20 mcg/kg/min) • Levophed + 0.05 mcg/kg/min per 10 minutes until MAP OK (max 1 mcg/kg/min) 	
Step1: Fluid responsiveness?
 
 • Sinus: SVV > 12% • AF: Passive leg raising test 
7 Plasmalyte 500 cc/u (max 3l/24u)
 
Step2: Hemoglobin < 10 g/dl?
 
7 Transfusion 1 UPC
 
Step3: Heartrate < 40 SPM
 
7 Consider Isuprel of Pacing
 
Step4: Inotropics/vasopression
 
 • Dobutamine + 5 mcg/kg/min (max 20 mcg/kg/min) 	
Step1: Fluid responsiveness?
 
 • Sinus: SVV > 12% • AF: Passive leg raising test 
7 Plasmalyte 500 cc/u (max 3l/24u)
 
Step2: Hemoglobin < 10 g/dl?
 
7 Transfusion 1 UPC
 
Step3: Heartrate < 40 SPM
 
7 Consider Isuprel of Pacing
 
Step4: Inotropics/vasopression
 
 • Dobutamine + 5 mcg/kg/min (max 20 mcg/kg/min)

SVO₂ 65-75%	Levophed + 0.05 mcg/kg/min per 10 minutes until MAP OK (max 1 mcg/kg/min)	OK (recheck after 1hour)	Levophed - 0.05 mcg/kg/min per 10 minutes until MAP OK
SVO₂ > 75%	Levophed + 0.05 mcg/kg/min per 10 minutes until MAP OK (max 1 mcg/kg/min)	
Step1: Inotropics
 
 • Dobutamine - 5 mcg/kg/min 
Step 2: Seloken 5mg/5 min IV if HR > 90 SBM
	
Step1: Inotropics/Vasopressors
 
 • Dobutamine - 5 mcg/kg/min • Levophed - 0.05 mcg/kg/min per 10 minutes until MAP OK 
Step 2: Seloken 5mg/5 min IV if HR > 90 SBM

Table 1: Hemodynamic interventions

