In case of below target SVO₂, fluid status will be optimized if fluid responsiveness is anticipated as indicated by stroke volume variation (if sinus rhythm, full sedation, normal TV ventilation) or passive leg raising test (step 1), anemia will be corrected to maintain a hemoglobin above 10 g/dl (step 2), treatment of excessive bradycardia (heart rate <40 BPM) will be considered (step 3) and dobutamine will be infused (step 4) according to the study protocol. Additional fluid challenge will be limited to 3 liters/24 hours.

In case of below target MAP but normal SVO₂, norepinephrine will be infused.

In case SVO₂ exceeds 75%, dobutamine infusion rate will be reduced (step 1) and seloken 5mg IV (1mg/min) will be infused if heart rate exceeds 90 BPM and MAP 100mmHg in the absence of inotropic or vasopressive support (step 2).

In case MAP is greater than 100mmHg, norepinephrine infusion rate will be reduced (step 1) and seloken 5mg IV (1mg/min) will be infused if heart rate exceeds 100 BPM and SVO₂ 75% in the absence of inotropic or vasopressive support (step 2). In the intervention (“Neuroprotect post-CA”) group, a reduction in vasopressor doses to maintain a MAP of 65mmHg is recommended if any of the pre-specified serious adverse events that were potentially related to an increased rate of vasopressor infusion occurs. These events include: major ventricular arrhythmia requiring life support, electrical or pharmacological cardioversion, poorly tolerated supraventricular arrhythmia and peripheral limb ischemia.

In patients randomized to receive current standard of care, hemodynamic support will be at the discretion of the treating physician with a target MAP of 65mmHg. All the drugs used in the study will be purchased from manufacturers not involved in the study.

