## 11.6 Safety Outcomes

The number (%) of patients with safety outcomes (i.e. incidence of life-threatening arrhythmias, limb ischaemia, new onset atrial fibrillation, pulmonary congestion requiring diuretics) will be presented by actual group for the SS.

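### A poorly tolerated supraventricular arrhythmia other than new-onset AF can end the higher pressure target yet have no row in the planned safety table, and target lowering itself is not counted

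*Protocol*

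**What the plan says.** **Events that lower the target.** Protocol 6.3.3, repeated in 6.5.1, applies to the intervention arm only: "a reduction in vasopressor doses to maintain a MAP of 65mmHg is recommended if any of the pre-specified serious adverse events" occurs. It describes these as "pre-specified serious adverse events that were potentially related to an increased rate of vasopressor infusion" and lists them: "These events include: major ventricular arrhythmia requiring life support, electrical or pharmacological cardioversion, poorly tolerated supraventricular arrhythmia and peripheral limb ischemia". The list can be read in two ways. Cardioversion may be a trigger of its own, or it may only qualify the ventricular arrhythmia.

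**Events named as safety outcomes.** Protocol 6.8.2 and SAP 2.2.3 name three: life-threatening arrhythmia (not defined), new-onset AF ("Incidence of new onset atrial fibrillation during intervention period"), and pulmonary congestion that needs diuretics. The hourly record in Protocol 6.6.3 has these three plus limb ischaemia. SAP 11.6, the only safety table in the SAP, has the same four: "life-threatening arrhythmias, limb ischaemia, new onset atrial fibrillation, pulmonary congestion requiring diuretics".

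**General capture.** Protocol 7.3 puts every adverse event of the intervention period on the case report form, with severity, relationship and management. Protocol 7.3.2 sends serious events to the coordinating centre and the DSMB. The SAP names no table of adverse or serious adverse events.

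**Lowering of the target.** SAP 8.1 lists randomisation, analysis sets, deaths, discharges and Day 180 status. It has no line for a lowered target or for stopped study treatment. SAP 6.1 and 11.6 summarise safety by actual treatment and do not say how a patient lowered to 65 mmHg is classed.

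**The concern.** The protocol itself links certain harms to vasopressor escalation and makes them grounds for giving up the 85-100 mmHg target. One would expect each of them to appear in the planned safety analysis, together with the number of patients whose target was given up. One of the named harms is covered only in part, and the lowering is not counted at all.

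Affected patients are plausible. A history of arrhythmia is a baseline item (Protocol 6.4) and not an exclusion, and Table 1 has a branch for AF ("AF: Passive leg raising test"). This is only indirect support, because that branch applies equally to AF that begins after the arrest, and the baseline item is not specific to AF.

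Two things are at stake. The trial report could omit a harm that the protocol ties to the strategy. It could also fail to say how often the strategy had to be abandoned, which bears on tolerability and, because a lowered patient moves to the control target, on how a null primary result is read.

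**Working it through.** The documents state no safety event rate, so there is no figure of the plan to reproduce. The check is a comparison of lists.

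**Step 1. Trigger events against planned counts**

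| Trigger (Protocol 6.3.3, 6.5.1) | Hourly record (Protocol 6.6.3) | Outcome lists (Protocol 6.8.2, SAP 2.2.3) | Safety table (SAP 11.6) |
|---|---|---|---|
| Major ventricular arrhythmia | Yes, as life-threatening arrhythmia | Yes, same | Yes, same |
| Limb ischaemia | Yes | No | Yes |
| Poorly tolerated supraventricular arrhythmia | Only if new-onset AF or judged life threatening | Same restriction | Same restriction |
| Cardioversion, if a separate trigger | No line of its own | No line | No line |
| The lowering of the target | No item | No | No, and not in SAP 8.1 |

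Of the three clearly named clinical events, two are tabulated and one is tabulated in part. The action taken is counted nowhere.

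**Step 2. Follow one patient.** Suppose an intervention patient has poorly tolerated flutter that nobody labels life threatening, and the target is lowered.

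- The event goes on the adverse event page and, as a serious event, to the DSMB (Protocol 7.3, 7.3.2).
- It fits no row of SAP 11.6.
- The lowering follows the protocol, so it need not be a deviation and need not show among the reasons for per-protocol exclusion in SAP 8.1.
- Norepinephrine dose is recorded hourly (Protocol 6.6.2) and arterial pressure continuously (6.6.1). SAP 11.1 summarises hourly data by group and time point, which cannot show who was lowered or why.

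The event and its management should therefore be on file, but neither has a planned route into the results.

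**Step 3. How many patients might be affected.** This is an illustration on assumed rates. Let p be the proportion of intervention patients with a supraventricular event that has no row, and take the planned 56 per arm (Protocol 6.9.1). The expected number is 56 × p, and the chance of at least one is 1 − (1 − p)^56.

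| Assumed p | Expected number | Chance of at least one |
|---|---|---|
| 2% | 56 × 0.02 = 1.1 | 1 − 0.98^56 = 68% |
| 5% | 56 × 0.05 = 2.8 | 1 − 0.95^56 = 94% |
| 10% | 56 × 0.10 = 5.6 | 1 − 0.90^56 = 99.7% |

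These figures say how many events could lack a row. They say nothing about the difference between arms.

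**Step 4. Classification by actual treatment.** SAP 6.1 gives no rule for a patient whose target was lowered to the control value. If such a patient were classed as control, the event that caused the lowering would move to the wrong arm. The SAP does not say that this will be done, but it does not exclude it.

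**The case against.** **The data are collected.** Protocol 7.3 covers every adverse event and its management, and 7.3.2 takes serious events to the DSMB. Lowering the target because of an event is management of that event. This stands, and it confines the point to planned tabulation.

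**Most triggers are counted.** Major ventricular arrhythmia falls under life-threatening arrhythmia, and limb ischaemia is in SAP 11.6. This also stands. A reader might infer that the harms that end the higher target are, as a group, left uncounted. The documents contradict that.

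**Understatement is not shown.** A reader might also infer that harm of the strategy is understated. One could assume true rates of 15% and 5% with one third of events missed. The counted rates would be 15% × 2/3 = 10% and 5% × 2/3 = 3.3%, so the excess would shrink from 10 to 6.7 points. This does not hold up:

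- All the inputs are assumptions.
- The AF outcome has no tolerance condition, so well-tolerated new-onset AF is counted too. Counted events are not a subset of poorly tolerated ones, and the counted rate could lie above or below the assumed true rate.
- The same definitions apply in both arms, and even in that example the risk ratio stays at 3.

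**What remains.** The SAP's only safety analysis is the four-row table, and nothing in the SAP brings the captured supraventricular events or the lowered targets into the report.

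**Conclusion.** The point holds as a gap in planned reporting. A poorly tolerated supraventricular arrhythmia that is neither new-onset AF nor judged life threatening has no row in the safety analysis, although the protocol makes it a reason to lower the target. Lowering of the target is counted in no planned table. The safety lists also disagree on limb ischaemia, which is in SAP 11.6 but not in Protocol 6.8.2 or SAP 2.2.3.

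The size and direction of any effect on the comparison between arms cannot be computed from the documents. The 1.1 to 5.6 patients in the working rest on assumed rates of 2% to 10% and describe events without a row, not bias. The primary analysis is untouched. The change is worth making because it is cheap and concerns a harm the protocol itself ties to the strategy.

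**What to change.** - **Safety outcomes.** Keep new-onset AF as its own outcome, because replacing it would lose well-tolerated cases that are now counted. In SAP 2.2.3 and 11.6, and in Protocol 6.8.2, add a row for any poorly tolerated supraventricular arrhythmia, new or recurrent, and a combined row for any 6.3.3 event. Add limb ischaemia to the two lists that lack it. State whether cardioversion is a trigger of its own, so that the combined row is well defined.
- **Source and presentation.** Take the new rows from the adverse event and serious adverse event pages already collected. Show them by randomised arm with risk difference and 95% confidence interval.
- **Classification.** State in SAP 6.1 that a patient whose target was lowered under 6.3.3 stays in the intervention group for the summaries by actual treatment.
- **Target lowering.** Add to SAP 8.1 the number, timing and reason of target lowering in the intervention arm, derived from adverse event management entries and the arterial pressure and norepinephrine records.

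The cost is a few table rows and some retrospective derivation, preferably done without knowledge of outcome. SAP 4.2 shows that inclusion was complete by the blinded review of 5 March 2018. New case report form items would come too late, and some reasons may be incomplete. The clinical rule for lowering the target is not changed.
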